7.7 EXTENT OF EXPOSURE

Standard descriptive analyses over all treatment courses will be performed. This will include a summary of the variables already described in [Section 5.4.2](#). This descriptive analysis will comprise a mixture of frequency and percentages, as well as summary statistics.

For the sequence of doses, there will be a listing of each dose taken at each treatment course for all patients.

7.8 SAFETY ANALYSIS

The primary analysis is for determination of MTD. No statistical model is foreseen allowing assessment of MTD; descriptive analysis is confined to a listing by dose group. The purpose of these tables is to summarize and document the data that led to the selection of the MTD.

With regard to the final CTR, no selected MTD analyses for Caucasian patients will be displayed since the determination of the MTD for Caucasian patients has been already described in the “CTR – Phase I Safety Analysis Report” see (8)).

7.8.1 Adverse events

7.8.1.1 Maximum tolerated dose and dose limiting toxicity

A summary of the number of patients with DLT within the MTD evaluation period will be given by initial treatment.

In order to explore the behaviour of DLTs with respect to the actual dose of BI 836826, we will examine descriptively the dose response relationship, using DLTs in the MTD evaluation period and DLTs up to the end of the on treatment phase, in separate analyses. Still, the determination of the MTD of Caucasian patients had been already described in the “CTR – Phase I Safety Analysis Report” (8) and will thus not be described again in the final CTR.

7.8.1.2 Adverse events

AE analysis will be performed for all treatment periods and selected analyses for the MTD evaluation period.

The analyses of AEs will be descriptive in nature and will follow the standard procedure laid down in the Data Management and Statistics Manual (DM & SM) (including all required tables and listings) (current guideline 'Handling and Summarization of AE Data for CTR and Integrated Summaries' (6)). AEs will be coded with the most recent version of Medical Dictionary for Regulatory Activities (MedDRA). The version number will be displayed as a footnote in the respective tables and listings. The SOC will be sorted alphabetically, and PTs will be sorted by descending frequency of adverse events in the "Total" BI 836826 group

Each patient can be observed during the trial under several doses. Analysing the AE of all treatment courses will be carried out under the initial treatment. No formal statistical analysis is planned for the safety comparison.

The analysis of AEs will be based on the concept of treatment emergent AEs. That means that all AEs occurring between the first administration of BI 836826 until 8 weeks after last administration of BI 836826 will be assigned to the on-treatment period. AEs will be distinguished for the treatment course in which the subjects are on-treatment as well as for screening, and post-study. The actual planned dosage of BI 836826 administered on the day each AE starts will also be derived and will be included in the listing. Listings of screening events will not be sorted by initial treatment. Post-study listings will be sorted by initial treatment.

According to the BI standards, multiple recordings of AEs will be collapsed to episodes on the lowest level term and multiple episodes will be condensed to records on the PT and SOC level. CTCAE grade will be an additional criterion for collapsing and condensing AEs. The maximum CTCAE grade will be assigned to episodes and records. CTCAE grade and DLT information will be displayed in AE listings. MedDRA levels for condensing will be SOC and PT.

CTCAE grading within AE tables is displayed as "all Grades", "Grade 1", "Grade 2", "Grade 3", "Grade 4" and "Grade 5". AEs with missing CTCAE or CTCAE grades not equal to 1 to 5 will be displayed under the category "all grades", but no category "missing grade" is displayed. A footnote is explaining that AEs with missing CTCAE or CTCAE grades not equal to 1 to 5 will be displayed under the category "all grades" and therefore the separate categories might not sum up to the category "all grades". A separate table will show AEs leading to death. In this table no CTCAE grades will be shown. In the appendix (Section 16.1.9.2), the categorization "all grades", "missing grades", "Grade 1/2", "Grade 3/4" and "Grade 5" is used, but the "missing grade" column should only be displayed in case AEs with a missing CTCAE grade occurred.

AE attributes

AE attributes "CTCAE Grade 3/4 combined with drug relation" and "CTCAE Grade 5 combined with drug relation" will be derived to avoid incorrect condensing. Consider, for instance, a patient with coincident drug-related abdominal pain with CTCAE Grade 1, and non-related vomiting with CTCAE Grade 3. Without the new attribute these AEs would be reported as drug-related Grade 3/4 under the SOC Gastrointestinal Disorder. With the new AE attribute these AEs would be excluded.

Additional AE attributes "Drug relationship combined with seriousness of the AE" is needed similarly to the AE attribute "CTCAE Grade 3/4 combined with drug relation" and "CTCAE Grade 5 combined with drug relation", respectively, as described above.

Frequency of patients with AEs will be summarised by treatment, highest CTCAE grade, primary SOC and PT. Tables will be provided for patients with related AEs, with serious adverse events (SAEs), with non-serious AEs, with DLTs, with protocol-specified significant AEs, with other significant AEs, with Adverse events of special interest (AESIs), AEs by user-defined AE category, with Infusion-related reactions (IRRs), with AEs leading to permanent discontinuation of study medication, with AEs leading to dose reduction, and with AEs leading to death.

7.8.1.3 Protocol-specified significant AEs and AEs by user-defined category (UDAEC)

Protocol-specified significant AEs as defined in the CTP, Section 5.2.2.1, will be summarized..

AEs by UDAEC will be displayed in a frequency table of AEs by user-defined category, preferred term and worst CTCAE grade as well as in a frequency table by user-defined category and worst CTCAE grade. UDAEC categories are described in [Section 9.4](#).

7.8.1.4 Other significant AEs

Other significant AEs are serious and non-serious AEs leading to treatment discontinuation and/or serious and non-serious AEs leading to dose reduction. Respective frequency tables by worst CTCAE grade, primary system organ class and preferred term will be provided.

7.8.1.5 Infusion-related reactions (IRR)

Frequency of IRRs will be displayed in separate listings and tables where it will be differentiated between the reported AE term "Infusion-related reaction" and the symptoms of an IRR that are reported as AEs.

For patients at the beginning of this trial (up to the 50 mg dose cohort (enrolment before April 2013)), the symptoms of an IRR are reported as AEs but not captured explicitly as symptoms of an IRR. For these patients, potential symptoms of an IRR can be only identified by pre-defined AE preferred terms as given by the user-defined category . For patients from following dose cohorts (including some patients of the 50mg cohort), not only IRRs are reported with the AE term "Infusion-related reaction" but also its symptoms which are

additionally marked as symptoms of an IRR. IRR tables capturing IRR symptoms can be only displayed for these patients. A listing will show all patients with IRR episodes as well as reported symptoms of these IRRs. Furthermore symptoms of IRRs will also be displayed where it will be distinguished between symptoms marked as such and potential symptoms of an IRR.

The number of episodes of IRRs as well as the frequency of its symptoms and CTCAE grades will be displayed graphically for those patients where the symptoms of an IRR are reported as such.

The frequency of the AE “Infusion-related reaction” episodes based on the preferred MedDRA term will be displayed by administration visit together with its CTCAE grade for all patients.

7.8.1.6 Tumour lysis syndrome

Potential clinical tumour lysis syndrome will be analysed via the UDAECs for TLS as defined in [Section 9.4](#).

In addition, screening for laboratory signs of cell destruction based on the laboratory values of uric acid, potassium, phosphorus and creatinine will be done as described in [Section 5.4.5.2](#).

7.8.2 Laboratory data

The analyses of laboratory data will be descriptive in nature and will follow the standard procedure laid down in the DM & SM (Guideline 'Display and Analysis of Laboratory Data' [\(7\)](#)).

Patients will be counted under the initial treatment. The analysis of laboratory data will use the same ‘analysing treatments’ as described for the AEs, except for that the baseline laboratory value (as defined in [Section 6.7](#)) will be included in the ‘on-treatment’ period. Patients having at least one post-baseline laboratory value will be displayed in the descriptive analyses.

Single time courses by initial treatment will be used to display laboratory values over time. The graphs may be truncated if sufficient data is not available. These graphs will be displayed in Chapter 16.1.9.2 of the CTR for the following parameters, using the BI standardized values for haematology and differentials.

Haematology: haemoglobin, WBC count and platelets

Differentials: neutrophils (absolute count), absolute lymphocyte count, absolute Monocyte count and Natural Killer (NK) cells, CD 4 T-cell count

Biochemistry: LDH.

Clinically relevant abnormalities (as defined in [Section 9.2](#)) will also be summarised.

The change of the laboratory value will be calculated for all laboratory parameters from baseline to the end of the treatment for the whole treatment duration. No post-study laboratory values will be considered.

Worst laboratory value and its CTCAE grade (highest CTCAE grade) over all courses will be calculated for each laboratory parameter.

The change of the CTCAE grade of the lab value will be calculated

- from baseline to the last laboratory value on treatment
- from baseline to the worst value on treatment
- from worst value on treatment to last value on treatment

Note: For calculating the change in CTCAE grade from baseline, patients with a CTCAE grade of -9 (no CTCAE grade defined) will be treated as a CTCAE grade 0 for all analyses. In laboratory listings, the CTCAE grade is displayed as -9.

For Uric Acid and Hypokalemia, the CTCAE grade cannot always be assigned by the laboratory parameter itself as two different CTCAE grades have the same laboratory constellation, but are distinguished by additional clinical parameter. In this case a CTCAE grade of -1 will be assigned initially. Patients with a CTCAE grade of -1 will be treated as

- Grade 1 for Uric Acid
- Grade 1 for Hypokalemia

for all analyses. In laboratory listings, the CTCAE grade will be displayed as -1.

Patients with hepatic enzyme elevation will be tabulated.

Patients with possibly clinically significant laboratory values will be tabulated (see [Section 9.2](#)).

The prioritized laboratory values (see [Section 5.4.5.1](#)) will be displayed in Section 15 of the final CTR while all other laboratory parameters will be displayed in the Appendix of the CTR.

Neutropenia, thrombocytopenia and leukopenia

Episodes of low neutrophil, platelet and WBC counts are of special interest. Episodes with CTCAE grade 3/4 as well as episodes with CTCAE grade 4 lasting 7 or more days will be analysed separately.

An episode of low blood counts of grade 4 starts with the first occurrence of a CTCAE grade 4 and lasts until the first time the CTCAE grade falls back to <=3 (analogously for an episode of CTCAE grade 3/4).

In case the episode starts during the EOT or Follow-up, the duration of this episode is defined to be missing. The reason for this approach is that after the EOT laboratory data is only

captured infrequently and therefore the duration of an episode would be overestimated due to lack of data.

If an episode starts before EOT and the CTCAE grade of the respective parameter does not fall back to the respective grade that ends the episode and the patient dies, the end of the episode is defined by the date of death. If the episode starts before EOT and lasts during Follow-up, the episode is censored with the date of DBL.

Number of patients with respective episodes, number of episodes, episodes per patient, duration of individual episode, number of episodes divided by number of infusion per patient, mean and median duration of episode per patient will be displayed.

Additionally, a frequency table displaying number of patients with episode of neutropenia Grade 4 and concomitant AEs in the UDAEC Infections (incl. respiratory infections and sepsis) of any grade as well as only for Grade 3 or 4 infections will be provided. In this context, concomitant AE is defined as AE with onset date within the neutropenia episode. This will be also done for CD4+ T-cell count Grade 4 and concomitant CD4 related specific infections from the UDAEC CD4 related specific infections.

The same way, a frequency table displaying number of patients with episode of thrombocytopenia Grade 4 and concomitant AEs in the UDAEC bleeding of any grade as well as only for Grade 3 or 4 bleeding will be provided.

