6.7 BASELINE, TIME WINDOWS AND CALCULATED VISITS

Study days and visits will be labelled according to the flow chart of the CTP.

Unless otherwise specified, baseline is defined as the time-point closest to but prior to first administration of trial medication in the first treatment phase, where the first administration

of trial medication is defined in [Section 6.3](#) above. If this criterion is not fulfilled, then no baseline will be derived.

For laboratories where not only the examination date but also time is recorded, examination time has to be taken into account when defining baseline. That is, a laboratory value on the same date as the first study drug administration is considered as baseline value if and only if the time of laboratory value is before or the same as the date and time of the start of first study drug administration.

If any of these times are missing (either no time of start of first study drug administration or no lab sample stating that it was taken prior to start of first study drug administration) and so it cannot be concluded whether the blood sampling was done before or at the same time of the start of first study drug administration, the last available laboratory assessment before first study drug administration will be taken (Screening laboratory) .

For graphical presentations of laboratory data, baseline will be coded as Day = 1.

The definition of relative baseline for the investigation of laboratory signs of cell destruction is given in [Section 5.4.5.2](#).

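### SAP 7.8.2 counts the pre-treatment baseline laboratory value as on-treatment, so a pre-drug value can be reported as a patient's worst on-treatment value

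*SAP*

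**What the plan says.** SAP 7.8.2 applies the adverse-event treatment periods to laboratory data with one exception: the baseline value "will be included in the ‘on-treatment’ period". SAP 6.7 fixes what that value is: "baseline is defined as the time-point closest to but prior to first administration of trial medication in the first treatment phase". For timed samples, one taken at the very start of the first infusion still counts as baseline.

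SAP 7.8.2 then sets these derivations:

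- "Worst laboratory value and its CTCAE grade (highest CTCAE grade) over all courses will be calculated for each laboratory parameter";
- grade changes from baseline to the last on-treatment value, "from baseline to the worst value on treatment", and "from worst value on treatment to last value on treatment";
- the change in each parameter from baseline to the end of treatment, with post-study values left out;
- episodes of low neutrophils, platelets and white cells, each opening at the first value of the relevant grade.

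On who is shown, it says: "Patients having at least one post-baseline laboratory value will be displayed in the descriptive analyses".

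For adverse events, SAP 7.8.1.2 starts the clock at dosing: "all AEs occurring between the first administration of BI 836826 until 8 weeks after last administration of BI 836826 will be assigned to the on-treatment" phase. Protocol 7.3.3 does the same.

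**The concern.** A value taken before any drug cannot be an effect of the drug. Once it sits in the on-treatment period and nothing in the section takes it out again, the worst on-treatment value is a maximum over a set that includes baseline. A patient who enters with a poor count and improves on treatment would be tabulated with the entry count as the worst on-treatment result. The worst-to-last comparison would then show recovery from something that was present before the first infusion.

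The term on-treatment would also carry two meanings in one report, one for adverse events and one for laboratory data.

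Poor entry values are possible in this population. Protocol 3.3.3 admits platelets down to 25 x 10^9/L and neutrophils down to 1.0 x 10^9/L, and sets no entry limit for haemoglobin, white cells, lymphocytes or CD4 count. SAP 7.8.2 singles out low neutrophil, platelet and white cell counts as being of special interest. SAP section 3 ties the opening of the lower Korean dose cohorts to infections with Grade 4 neutropenia in 3 of 4 patients. These are tables that readers will look at closely.

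**Working it through.** The plan gives no figure for this point, so there is none to reproduce. The check is logical, followed by a scale.

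**1. Direction.** Let b be the baseline grade and p the worst post-baseline grade. The literal rule reports max(b, p); a post-baseline rule reports p. Since max(b, p) ≥ p, the reported worst grade can only be too high. It is wrong only when b > p, that is, when baseline is worse than every later value.

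**2. Which tables change.** With grades 0 to 4 there are 5 x 5 = 25 pairs (b, p). These are counts of possibilities, not of patients.

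| Quantity | Baseline included | Baseline excluded |
|---|---|---|
| Pairs in which the reported worst grade exceeds p | 10 | 0 |
| Pairs showing worsening from baseline | 10 | 10 |
| Pairs showing improvement, baseline to worst | 0 | 10 |
| Pairs with worst grade ≥ 3 | 16 | 10 |

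Worsening is unchanged because max(b, p) > b exactly when p > b. Improvement disappears because max(b, p) can never be below b.

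For worst-to-last, take b = 3 and all later values Grade 1. The literal rule shows 3 to 1, a recovery. The post-baseline rule shows 1 to 1, no change.

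**3. When the Grade 3/4 rate moves.** Of the 10 pairs with b > p, only those with b in {3, 4} and p in {0, 1, 2} cross the line: 2 x 3 = 6, which is 16 − 10 above. The other four (1 to 0, 2 to 0, 2 to 1, 4 to 3) change the reported grade but not the Grade 3/4 count.

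**4. Size per patient.** One patient of the step 3 type adds 1/n to the rate: 1/3 = 33% and 1/6 = 17% in cohorts of 3 and 6, and 1/37 = 2.7% among the 37 Caucasian patients (SAP section 3). This is what one such patient would do, not an expected bias.

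**5. Size overall, on assumptions.** Let a be the share with baseline Grade 3 or higher and r the share of those whose later values are all Grade 2 or lower. The overcount in the rate is a x r, and in patients N x a x r. Protocol 7.6 expects N = 41 + 12 = 53. The documents give neither a nor r, so I assume a from 0 to 20% and r from 0 to 50%:

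- lowest: 0 points, 0 patients;
- a = 10%, r = 30%: 0.10 x 0.30 = 3 points; 53 x 0.03 = 1.6 patients;
- highest: 0.20 x 0.50 = 10 points; 53 x 0.10 = 5.3 patients.

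**6. Episodes.** If the baseline record may open an episode, a baseline value of the qualifying grade followed by a better one adds an episode. If the low count persists after dosing, the number of episodes is the same but the start is earlier. The cross-tables with infections and bleeding are built on these episodes.

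**7. What is untouched.** DLTs are drug-related non-haematological adverse events (Protocol 5.2.1.1), and the MTD rests on them (SAP 5.1 and 7.4). The screen for laboratory signs of cell destruction uses its own baseline before each infusion (SAP 5.4.5.2). The change from baseline to end of treatment uses neither the worst value nor the episodes.

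**The case against.** The best defence is that baseline is carried into the on-treatment data only for display and as a reference. The shift analyses name baseline and the worst on-treatment value as separate ends, and a patient needs a post-baseline value to be shown at all. SAP 7.8.2 also defers to an internal laboratory guideline, which may already restrict the worst value.

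This reading is possible but not established. The exception is written for the laboratory analysis as a whole, not for a plot or listing. The post-baseline condition selects patients; it does not say which of their records enter the maximum. The section states an exclusion for post-study values and has no counterpart for pre-treatment ones. The guideline was not available, so one can say only that nothing shown removes the baseline record.

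Other parts of the defence stand. Improvement remains visible in the change from baseline to end of treatment and in the grade change to the last value. Protocol 3.3.3 excludes AST, ALT and bilirubin of Grade 2 or higher, which limits the effect for those parameters. The neutrophil floor also limits it, though the documents do not print the CTCAE thresholds that would show how far.

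A reader might infer that the dose recommendation is distorted, because Protocol 5.2.1.1 brings cytopenias into the choice of dose for further development. That text refers to haematological adverse events, whose on-treatment period starts at first dosing. The documents show no route from the worst-laboratory tables to a dose decision.

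**Conclusion.** The point holds as a gap in a descriptive definition. On the literal text, a pre-drug laboratory value can be reported as the worst on-treatment value. The stand-alone worst-grade summaries, the worst-to-last shift and possibly the cytopenia episode counts can then be overstated and cannot be understated, and the baseline-to-worst shift loses all improvement.

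It would go too far to conclude that on-treatment laboratory toxicity is overstated in this trial. That needs patients whose baseline is worse than everything later, and the documents do not say how many there are. Nor does every such patient move a small cohort's Grade 3/4 rate by 17 to 33 points; only one going from Grade 3 or 4 to Grade 2 or lower throughout does. The 0 to 10 point range rests wholly on assumed inputs and starts at zero.

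Severity is minor: no formal tests are planned (Protocol 7.2), and the primary endpoint and all counts of worsening from baseline are the same under either reading.

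**What to change.** Add to SAP 7.8.2 that the baseline value is kept in the on-treatment data set only for display and as the reference for change. Add that worst value, worst CTCAE grade, last on-treatment value and the onset of cytopenia episodes are derived only from samples taken after the start of the first administration of BI 836826. For the last value this changes little, since displayed patients must already have a post-baseline sample, but it keeps the rule uniform.

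The cost is one or two sentences and a filter in the programs. If the internal guideline or existing programs already do this, the text simply records it.
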